Appendix 2. FACIT-Fatigue Scale (Version 4) and Scoring Guidelines

FACIT-Fatigue Scale (Version 4)

Below is a list of statements that other people with your illness have said are important. **Please circle or mark one number per line to indicate your response as it applies to the past 7 days.**

		Not at all	A little bit	Some- what	Quite a bit	Very much
HI7	I feel fatigued	0	1	2	3	4
HI12	I feel weak all over	0	1	2	3	4
An1	I feel listless (“washed out”)	0	1	2	3	4
An2	I feel tired	0	1	2	3	4
An3	I have trouble starting things because I am tired	0	1	2	3	4
An4	I have trouble finishing things because I am tired	0	1	2	3	4
An5	I have energy	0	1	2	3	4
An7	I am able to do my usual activities	0	1	2	3	4
An8	I need to sleep during the day	0	1	2	3	4
An12	I am too tired to eat	0	1	2	3	4
An14	I need help doing my usual activities	0	1	2	3	4
An15	I am frustrated by being too tired to do the things I want to do	0	1	2	3	4
An16	I have to limit my social activity because I am tired	0	1	2	3	4

FACIT-Fatigue Subscale Scoring Guidelines (Version 4)

Instructions:

- 5) Record answers in "item response" column. If missing, mark with an X.
- 6) Perform reversals as indicated, and sum individual items to obtain a score.
- 7) Multiply the sum of the item scores by the number of items in the subscale, then divide by the number of items answered. This produces the subscale score.

8) The higher the score, the better the QOL.

Subscale	Item Code	Reverse Item?	Item Response	Item Score	
Fatigue Subscale	HI7	4 -	_____	= _____	
	HI12	4 -	_____	= _____	
	Score range: 0 – 52	An1	4 -	_____	= _____
		An2	4 -	_____	= _____
		An3	4 -	_____	= _____
		An4	4 -	_____	= _____
		An5	0 +	_____	= _____
		An7	0 +	_____	= _____
		An8	4 -	_____	= _____
		An12	4 -	_____	= _____
		An14	4 -	_____	= _____
		An15	4 -	_____	= _____
	An16	4 -	_____	= _____	
			Sum individual item scores:		= _____
			Multiply by 13:		= _____
			Divide by number of items answered:		= _____
				= Fatigue Subscale score	

Appendix 3. Oral Corticosteroids Dose Conversion Chart

The following table will be used for converting non-prednisone medications to prednisone equivalent:

*Example: Subject is taking 8 mg of Methylprednisolone orally daily. To get the equivalent dose of prednisone: 8 mg Methylprednisolone = $(5*8)/4 = 10$ mg prednisone.*

Corticosteroids Name	Equivalent Dose (mg) to 5 mg Prednisone
Deflazacort	7.5 mg
Methylprednisolone	4 mg
Prednisolone	5 mg
Prednisone	5 mg
Triamcinolone Acetonide	4 mg

Appendix 4. Sample SAS Code for Analysis of Binary Endpoints

The following model statement will be used to construct the confidence interval for the binomial proportion difference described in Section 6.3.2:

```
proc freq data = test ;  
  by avisitn;  
  tables TRT01PN*aval_ / riskdiff (CORRECT);  
  output out = f200vp_ci RISKDIFF;  
  where TRT01PN = 1 | TRT01PN = 3;  
run;
```

where the confidence interval for the difference of two independent binomial proportions is constructed based on the normal approximation (ie, the Wald method) with a continuity correction, to adjust for the difference between the normal approximation and the binomial distribution, which is a discrete distribution:

$$(\hat{p}_1 - \hat{p}_2) \pm \left(\frac{1}{2} \left(\frac{1}{n_1} + \frac{1}{n_2} \right) + z_{\alpha/2} \times \sqrt{\frac{\hat{p}_1(1 - \hat{p}_1)}{n_1} + \frac{\hat{p}_2(1 - \hat{p}_2)}{n_2}} \right)$$

The following model statement will be used to construct the confidence interval for the binomial proportion described in the Section 6.3.2:

```
proc freq data = test ;  
  by avisitn TRT01PN;  
  tables aval_ / BINOMIAL (CORRECT);  
run;
```

the confidence interval for the binomial proportions is constructed based on the normal approximation to the binomial distribution with continuity correction:

$$\hat{p}_1 \pm \left(\frac{1}{2} \left(\frac{1}{n_1} \right) + z_{\alpha/2} \times \sqrt{\frac{\hat{p}_1(1 - \hat{p}_1)}{n_1}} \right)$$

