1.3. Sample Size and Power

Sample size is determined based on the non-inferiority test of each filgotinib group compared to the adalimumab group on the ACR20 response rate at Week 12. When assuming the ACR20 response rate being 52% and 60% for the adalimumab and each filgotinib group, and 38.6% for the placebo group, 244 subjects in each filgotinib group and placebo group, and 122 subjects in the adalimumab group are required to obtain 90% power at a two-sided 0.025 significance level to demonstrate that filgotinib group preserves more than 50% of the effect of adalimumab with respect to the ACR20 response rate at Week 12.

A sample size of 244 subjects in each filgotinib group and the placebo group will provide over 95% power to detect a difference in ACR20 response rate of 21.4% at Week 12 (38.6% and 60% for the placebo group and each filgotinib group, respectively) using a two-sided 0.025 significance level superiority test.

In summary, the total sample size will be approximately 854 subjects per original planning.

The study was terminated per Sponsor’s decision after 67 subjects had been enrolled. At study termination, 13 out of 67 subjects continued on to the LTE, and 7 of those 13 subjects were terminated immediately after entering LTE phase. All the other subjects were prematurely discontinued from or completed the Main Study visits.

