6.3.2. Analysis Methods for Key Secondary Efficacy Endpoints

For the superiority test of filgotinib 200 mg or filgotinib 100 mg group versus placebo control group in binary key secondary endpoints such as the ACR50 response rate at Week 12, the PASI75 response rate at Week 16 in subjects with psoriasis covering $\geq 3\%$ of the BSA at Baseline and the MDA response rate at Week 16, the observed response rate and 2-sided 95% CI based on normal approximation with continuity correction will be provided by visit. Non-stratified response rate difference along with its 95% CI calculated based on the normal approximation with continuity correction will be provided. Appendix 4 provides sample SAS models statements for constructing the confidence interval for the proportion. In addition, the p-value based on the logistic regression model same as the one used in section 6.2.2 with observed cases for testing the superiority of filgotinib 200 mg or filgotinib 100 mg as compared to placebo will be provided as well. In case of limited data leading to improper use of logistic model, the p-value will not be provided.

For non-inferiority test of filgotinib 200 mg or filgotinib 100 mg group versus adalimumab group in the ACR20 response rate at Week 12, the approach proposed by {Liu 2014} will be used to demonstrate that each filgotinib dose preserves more than 50% of the effect of adalimumab on the response rate of ACR20 at Week 12. Let π_T , π_C and π_P denote the true response rates of ACR20 for filgotinib, adalimumab and placebo, respectively, at Week 12, with corresponding variances σ_T^2 , σ_C^2 and σ_P^2 . The non-inferiority hypotheses are

$$H_{0,NI} : \frac{\pi_T - \pi_P}{\pi_C - \pi_P} \leq 0.5$$

vs

$$H_{1,NI} : \frac{\pi_T - \pi_P}{\pi_C - \pi_P} > 0.5$$

According to {Liu 2014}, the test statistics for non-inferiority (filgotinib preserves more than 50% of the effect of adalimumab) is

$$Z_{NI} = \frac{\hat{\pi}_T - 0.5\hat{\pi}_C - (1 - 0.5)\hat{\pi}_P}{\sqrt{\hat{\sigma}_T^2 + 0.5^2\hat{\sigma}_C^2 + (1 - 0.5)^2\hat{\sigma}_P^2}}$$

Note that the “hat” (^) denotes the estimated values of each parameter at Week 12. Missing data will be imputed using multiple imputation (MI) assuming that missing data are missing at random (MAR), which will follow the same method as described for the primary endpoint.

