6.4.2. Analysis Methods for Other Secondary Endpoints

The FAS will be used for all summaries and analyses of other secondary efficacy endpoints.

For the binary endpoints of the ACR20 response, the ACR50 response, the PASI75 response in subjects with psoriasis covering $\geq 3\%$ of the BSA at Baseline and the MDA response, for subjects with observed outcome, the similar analysis as the key secondary endpoint analyses described in Section 6.3.2 will be applied. The proportions of subjects achieving above endpoints (observed case) will be plotted over time during Main study by treatment and by visit.

For all the other binary endpoints, only above mentioned observed response rate, 2-sided 95% CI and non-stratified response rate difference along with its 95% CI will be provided by visit.

For all the continuous endpoints, absolute value and change from Baseline will be summarized using descriptive statistics (sample size, mean, SD, median, Q1, Q3, minimum, and maximum) by treatment and by visit.

For the continuous endpoints of the change from baseline in HAQ-DI, the change from Baseline in SF-36v2 PCS, the change from Baseline in LEI for subjects with enthesitis at Baseline, the change from Baseline in FACIT-Fatigue and the change from Baseline in LDI for subjects with dactylitis at Baseline, plots of mean \pm SD for change from baseline by visit will be presented.

For time to event analyses, Kaplan-Meier plot of each treatment group during Main study will be provided. Number of subjects having events and censored, KM estimates of median (95% CI), Q1, Q3, minimum and maximum of the time to events will be summarized by treatment group.

The by-subject listing of each endpoint and corresponding components, if available, including data during the Main Study and LTE phases will be provided.

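### SAP Appendix 4 names no responder level and keeps no zero counts, so its one-sample code cannot return the observed response rate in every visit-by-arm group

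*SAP*

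**What the plan says.** For the binary key secondary endpoints (ACR50, PASI75, MDA), SAP Section 6.3.2 states that "the observed response rate and 2-sided 95% CI based on normal approximation with continuity correction will be provided by visit", together with an unstratified difference and its interval. It then points to the code: "Appendix 4 provides sample SAS models statements for constructing the confidence interval for the proportion". For the binary endpoints other than ACR20, ACR50, PASI75 and MDA, Section 6.4.2 says "only above mentioned observed response rate, 2-sided 95% CI and non-stratified response rate difference along with its 95% CI will be provided by visit".

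Appendix 4 is headed as sample code, but the sentence introducing the one-sample block is a commitment: "The following model statement will be used to construct the confidence interval for the binomial proportion described in the Section 6.3.2". The block groups the data with "by avisitn TRT01PN" and requests "tables aval_ / BINOMIAL (CORRECT"). The two-sample block runs by visit and requests "tables TRT01PN*aval_ / riskdiff (CORRECT").

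Neither block names the level that counts as a response, sets a sort order, or supplies counts with empty cells retained. The coding of aval_ is not given anywhere in the SAP. The printed formulas use p-hat without saying which outcome it refers to. There is no rule for a group in which only one outcome occurs.

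**The concern.** A one-sample binomial request must be told which outcome to estimate. If it is not told, the software chooses, and here it chooses again in each visit-by-arm group from whichever levels are present there. The text asks for the response rate, and the code does not guarantee it.

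The groups are small. The trial stopped "after 67 subjects had been enrolled", and the binary endpoints include several that few subjects are likely to meet: ACR70, PASI90, PASI100, VLDA and the remission definitions, some of them assessed from the early visits. A group with no responders is therefore a realistic event. For most of these endpoints Section 6.4.2 plans no p-value, so the rate, the difference and their intervals are the whole between-arm comparison. An arm with no remissions shown as 100% remission would reverse the message of that row.

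**Working it through.** No sample size, power or alpha figure in the plan depends on this code, so there is no stated figure to reproduce. The check traces what the statement estimates.

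**Inputs**
- Enrolled: 67 (SAP Section 1.3). Allocation 2:2:1:2 (SAP Section 3.3). Expected arms: 67 × 2/7 = 19.1 and 67 × 1/7 = 9.6, so about 19, 19, 10 and 19. Actual arm sizes are not given. Missing visits and the restriction of PASI to subjects with at least 3% body surface area would make some groups smaller.
- Interval formula (Appendix 4): p ± [1/(2n) + 1.96 × √(p(1 − p)/n)], with limits cut off here at 0 and 1.
- Software default (assumed, general knowledge of PROC FREQ): without a named level, the proportion is that of the first level in sort order among those present in the BY group.
- True response rates of 5%, 10% and 20%: assumed for illustration. The documents give no rates for the stringent endpoints.

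**What the one-sample code returns**

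| Responders / n | Intended | Responders sort first | Non-responders sort first |
|---|---|---|---|
| 0/10 | 0% (0 to 5%) | 100% (95 to 100%) | 100% (95 to 100%) |
| 0/19 | 0% (0 to 2.6%) | 100% (97.4 to 100%) | 100% (97.4 to 100%) |
| 4/10 | 40% (4.6 to 75.4%) | 40% (4.6 to 75.4%) | 60% (24.6 to 95.4%) |
| 7/19 | 36.8% (12.5 to 61.2%) | 36.8% (12.5 to 61.2%) | 63.2% (38.8 to 87.5%) |
| 19/19 | 100% (97.4 to 100%) | 100% (97.4 to 100%) | 100% (97.4 to 100%) |

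A binary variable has only two sort orders. With responders first, the code fails only where nobody responds. With non-responders first, it fails wherever there is at least one non-responder. No choice of coding alone makes it right in every group.

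**How often a group has no responders:** (1 − p)^n
- p = 5%: 0.95^19 = 0.377; 0.95^10 = 0.599.
- p = 10%: 0.90^19 = 0.135; 0.90^10 = 0.349.
- p = 20%: 0.80^19 = 0.014; 0.80^10 = 0.107.

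The chance that at least one of the four arms has none, for one endpoint at one visit, is 1 − [1 − (1 − p)^19]³ × [1 − (1 − p)^10]: 0.90 at 5%, 0.58 at 10% and 0.145 at 20%. For contrast, at the planning ACR20 rates in SAP Section 1.3 (60%, 60%, 52% and 38.6%) the corresponding chance at Week 12 is 0.0007. The exposure is therefore in the stringent endpoints and early visits.

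**The two-sample code.** If nobody responds in either arm, or everybody responds in both, the table has one column and no difference or interval is produced. For two arms of 19 with no responders the chance is 0.377² = 0.14 at 5% and 0.135² = 0.018 at 10%. The printed formula would give 0 ± ½(1/19 + 1/19) = 0 ± 5.3 percentage points.

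**The case against.** The case against is that this is sample code and visibly a fragment: a placeholder data set name and one hard-coded contrast. Its purpose is to fix the interval type, the text asks unambiguously for the response rate, and nothing in the SAP permits reporting non-response. The final programs may well differ, and the by-subject listings required by Section 6.4.2 would allow a 0% printed as 100% to be found. The default is a property of the software that the SAP does not state, and SAS was not run for this check. All of that stands and limits the size of the point. It does not remove it, because Appendix 4 commits to the statement, and run as printed the statement does not deliver what the text requires.

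Three stronger readings are tempting and are not supported:
- A reader might infer that nearly every group would print the complement. That needs non-responders to sort first, and the coding of aval_ is not shown.
- A reader might infer that the main efficacy conclusions are at risk. The primary analysis (Section 6.2.2) uses logistic regression with multiple imputation, the non-inferiority test (Section 6.3.2) uses its own Z statistic after imputation, and the logistic p-values come from a model. None uses this code, and all p-values are already declared nominal.
- A reader might infer that the two-sample code gives a wrong difference when both arms have the same single outcome. It gives none: the result is missing, not wrong.

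**Conclusion.** The point holds in a limited form. As printed, the one-sample code cannot return the observed response rate in every visit-by-arm group. At best (responders sort first) it is correct except in zero-responder groups, which are output as 100%. If non-responders sort first, it outputs the non-response rate wherever a non-responder is present.

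The effect is confined to the observed-case descriptive rates and intervals, mainly for ACR70, PASI90, PASI100, VLDA, remission and early visits. With about 19 or 10 subjects per arm, a given group has no responders with probability 38% or 60% at an assumed 5% rate, and 14% or 35% at an assumed 10% rate. This rests on the PROC FREQ default, on arm sizes inferred from 67 subjects at 2:2:1:2, and on response rates that are not in the documents. The change should be made: the error would sit in isolated rows that a spot check could miss, and correcting it is cheap.

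**What to change.** - Define aval_ and state which value is a response.
- Name that value with LEVEL= in BINOMIAL, and specify the responder column in RISKDIFF.
- Feed complete arm-by-response counts with zero cells retained. Naming the level is not sufficient alone, because it does not supply a level that is absent from the group.
- Where the procedure still returns nothing, compute the rate, difference and interval directly from the printed Appendix 4 formulas with p-hat = responders/n. Then 0/n is reported as 0%, and a comparison of none with none, or all with all, as a difference of 0 with its continuity-corrected interval.
- Check every 0/n and n/n row against the by-subject listings. If the SAP is already final, record the change in the clinical study report, as the SAP Introduction requires.

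The cost is two options, a count data set and a short fallback calculation. No data, estimand or design feature changes.

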Appendix 5. Determining Missing and Virtual visits due to COVID-19

This appendix describes the site collection of COVID-19 data as pertains to missed/virtual visits and the data processing algorithm used to determine which visits were missing and which visits were virtual.

Data collection

A COVID-19 supplement to the eCRF Completion Guidelines (CCG) was provided by data management to instruct clinical trial sites with respect to data entry expectations pertaining to scenarios related to the COVID-19 pandemic. If a visit was missed, sites should enter “Visit missed due to COVID-19.” If a visit was conducted virtually, sites should enter “Virtual visit due to COVID-19.”

Determination of Missed and Virtual visits

Natural Language Processing (NLP) was used to search the CRF comment fields to identify instances of “COVID-19” (or synonyms, see [Table 11-1](#)) and “Virtual” (or synonyms, see [Table 11-1](#)). The search terms are maintained in a global lookup and can be modified to tune the NLP model. For any comments with COVID-19 search terms, assign “Missed visit” or “Virtual visit” as follows

- i) If COVID-19 terms are identified through NLP and the visit date is missing then result is ‘Missed Visit’
- ii) If COVID-19 and Virtual terms are identified through NLP for a visit, then result is ‘Virtual Visit’. When there are multiple records for the same subject and the same visit, NLP will be based on multiple records to ensure 1 unique category per subject per visit
- iii) Otherwise result is missing

Table 11-1. Examples of search terms for “COVID-19” and “Virtual” used to identify missed and virtual visits.

Search terms for “COVID-19”	Search terms for “Virtual”
COVID19	VIRTUAL
CORONA	TELEMED
CORONAVIRUS	TELEHEALTH
PANDEMIC	TELEPHONE
OUTBREAK	REMOTE
CRISIS	TELEMEDICINE
LOCKDOWN	TELECONSULTATION
QUARANTINE	TELEPHONICALLY
SHELTER	PHONE
	HOME VISIT
	ZOOM
	SKYPE

Appendix 6. Lists of PsA Medications

1) List of bioDMARDs and Investigational bDMARDs (WHO Preferred Terms)

- ABATACEPT
- ADALIMUMAB
- ALEFACEPT
- BIMEKIZUMAB
- BRODALUMAB
- CERTOLIZUMAB PEGOL
- ETANERCEPT
- GOLIMUMAB
- GUSELKUMAB
- INFLIXIMAB
- IXEKIZUMAB
- SECUKINUMAB
- TOCILIZUMAB
- USTEKINUMAB

2) List of csDMARDs (WHO Preferred Terms)

- AZATHIOPRINE
- CICLOSPORIN
- HYDROXYCHLOROQUINE SULFATE
- IGURATIMOD
- LEFLUNOMIDE
- METHOTREXATE
- METHOTREXATE SODIUM
- SULFASALAZINE

3) List of Corticosteroids (WHO Preferred Terms)

- BETAMETHASONE ACETATE;BETAMETHASONE SODIUM PHOSPHATE
- BETAMETHASONE BUTYRATE PROPIONATE;MAXACALCITOL
- BETAMETHASONE DIPROPIONATE;BETAMETHASONE SODIUM PHOSPHATE
- BETAMETHASONE DIPROPIONATE;CALCIPOTRIOL
- CLOBETASOL
- CLOBETASOL PROPINOATE
- CORTISONE
- DEFLAZACORT
- METHYLPREDNISOLONE
- METHYLPREDNISOLONE ACETATE
- METHYLPREDNISOLONE SODIUM SUCCINATE
- PREDNISOLONE
- PREDNISOLONE VALEROACETATE
- PREDNISON
- TRIAMCINOLONE
- TRIAMCINOLONE ACETONIDE

4) List of NSAIDs (WHO Preferred Terms)

- ACECLOFENAC
- CELECOXIB
- CODEINE PHOSPHATE;IBUPROFEN
- DEXKETOPROFEN TROMETAMOL
- DICLOFENAC
- DICLOFENAC POTASSIUM

- DICLOFENAC SODIUM
- ESOMEPRAZOLE MAGNESIUM;NAPROXEN
- ETODOLAC
- ETORICOXIB
- IBUPROFEN
- KETOPROFEN
- LOXOPROFEN SODIUM DIHYDRATE
- MELOXICAM
- NABUMETONE
- NAPROXEN
- NAPROXEN SODIUM
- NIMESULIDE
- SULINDAC
- TENOXICAM

GS-US-431-4566-SAP-v1.0

ELECTRONIC SIGNATURES

Signed by	Meaning of Signature	Server Date (dd- <small>MMM</small> - <small>yyyy</small> hh:mm:ss)
PPD	Clinical Research eSigned	16-Jul-2021 23:30:19
PPD	Biostatistics eSigned	20-Jul-2021 00:37:49
